6. STUDY DESIGN

General Study Design and Justification of Design

This is an investigator-initiated, randomized, parallel design trial with one intervention arm (bicycle exercise followed by intensive lifestyle modification) and one standard-of-care arm in patients with newly diagnosed or medically untreated type 2 diabetes mellitus. The bicycle intervention at enrollment

comprises approximately two hours with pre- and post-preparations and 30 minutes of moderate physical activity on a bicycle. The whole study period takes one year for both arms. Subjects in the intervention arm will be contacted by the study psychologist by telephone on a weekly basis for coaching and follow-up. Actigraph data readout will occur at baseline, 3 and 6 months. Additionally, everyday physical activity will be assessed by the SIMPAQ questionnaire at baseline and 6 months. Regular routine follow-up visits will be done for both groups in the respective hospitals, outpatient clinics or by the subjects' responsible general practitioner to acquire data on vital signs, glucose values and medication as well as adverse events. See **Table 1** for further details.

[figure not shown]

Figure 1 Schematic overview of study enrollment and initial intervention.

Methods of Minimizing Bias

6.1.1 Randomization

Participants will be randomized into the “lifestyle intervention” or “conventional anti-diabetic treatment” arm using a computer-generated random number in the electronic data managing application secuTrial®. Participants will be randomized 1:1 to the study groups.

6.1.2 Blinding Procedures

Blinding of patients and study personal is not possible for this study.

7. STUDY POPULATION

Eligibility Criteria

Participants fulfilling all of the following inclusion criteria are eligible for the study

- Able to give informed consent as documented by signature (Appendix ICF)
- Type 2 diabetes diagnosed within the last two years according to the ADA-criteria
- Age \geq 18 years
- HbA1c \geq 7.5 %

The presence of any one of the following exclusion criteria will lead to exclusion of the participant:

- Clinically unstable patient as defined by the physicians on duty e. g. signs of new ischemia in the ECG, systolic blood pressure \geq 200 mmHg, fever \geq 38.5 °C, symptoms of SIRS or reduced vigilance.
- Anti-diabetic medication for \geq 24 hours
- Inability to perform a bicycle exercise during 30 minutes
- Previous lifestyle intervention by an endocrinologist
- Engagement in physical activity more than five times per week
- Enrollment in other interventional study

Recruitment and Screening

Patients are recruited after seeking medical consultation at the emergency room, medical outpatient clinic of the respective study centers or their general practitioners. Patients will be assessed and enrolled in the study by the study team.

Assignment to Study Groups

Patients are randomized to the intervention or the control arm using a computer-generated number after agreeing to participate in the study.

Criteria for Withdrawal/Discontinuation of Participants

Participants may withdraw or be withdrawn at any time. Subjects who discontinue participation may be replaced. Reasons for discontinuation are:

- Participant withdraws informed consent
- Participant does not comply with study treatment or the concomitant procedures. Non-compliance for this study is defined as completion of less than 50% of the training program during two weeks
- Pregnancy
- Participant is no longer willing to continue the study because of any reason
- The incidence or severity of adverse events (AEs) indicate a potential health hazard to the participant

Withdrawal will be documented in the database with all other study data.

8. STUDY INTERVENTION

Identity of Investigational Products (Treatment/Medical Device)

There is no investigational product nor medical device used.

8.1.1 Experimental Intervention

In this study's interventional group no drugs except for the patient's original medication and Metformin starting after 3 months are used. The 30 minutes bicycle exercise will be performed on a standard bike home trainer.

8.1.2 Control Intervention (Standard Treatment)

Standard therapy for type 2 diabetes usually consists of a variation of oral anti-diabetic medication and/or s. c. insulin therapy as well as a limited lifestyle intervention according to national and international guidelines (American Diabetes 2018)¹².

Administration of Experimental and Control Interventions

8.1.4 Control Intervention

The control arm for this study will receive standard type 2 diabetes treatment after study enrollment. This treatment usually consists of a limited lifestyle intervention and oral anti-diabetic medication (i.e. Metformin, SGLT2-inhibitors, DPP-Inhibitors, GLP-1-receptor agonists etc.) or insulin therapy.

Dose/Device Modifications

Therapy for the participants of the intervention group has to be reassessed if:

- glucose values remain elevated above 15 mmol/l for more than 7 consecutive days
- in case of symptomatic hyperglycemia or re-hospitalization

In these cases, standard of care according to national and international guidelines will be implemented.

Compliance with Study Intervention

Patients in the intervention arm will be motivated by a specially trained psychologist and provided with an actigraph to monitor daily step count, overall physical activity and the scheduled training sessions. Personal motivation for the training sessions will be supported through telephone interviews, during study visits and with continuous self-evaluation. If the bicycle exercise is not completed or completed partly, this will be documented in the CRF.

Data Collection and Follow-up for Withdrawn Participants

Participants may withdraw or be withdrawn at any time. Subjects who discontinue participation will not be replaced. Withdrawal will be documented in the database with all other study data. All gathered data and samples until withdrawal of informed consent will be used anonymously for analysis. Follow-up will not take place if the patient has withdrawn informed consent, in all other cases follow-up will take place as planned.

Trial-specific Preventive Measures

Participants of the bicycle and intensive lifestyle modification group will, in addition to the general clinical visits, be closely monitored and coached with weekly telephone calls, thereby ensuring appropriate glucose management. If needed, standard of care medical treatment will be initiated also in the interventional group. All patient specific data will be recorded in an electronic case report form (eCRF).

Patients who were randomized into the intervention group will be instructed in correct self-measurement of blood glucose by a member of the study team at study enrollment or on visit 2. They will receive a blood glucose monitor to document fasting glucose every morning during the first week of the study. This way the study team is able to supervise the metabolic situation and may start rescue medication if needed.

Concomitant Interventions (Treatments)

Permitted concomitant treatments are all medication the patient has taken prior to the initial visit. We expect no influence on the study by treatment of other diseases. Not permitted are any oral anti-diabetic drugs (except for Metformin) or Insulin for the intervention group, except in case it needs to be administered as rescue medication.

9. STUDY ASSESSMENTS

Study Flow Chart and Table of Study Procedures and Assessments

Please refer to **Table 1** and **Figure 1**.

Assessments of Outcomes

9.1.1 Assessment of Primary Outcome

Glycated hemoglobin A1c will be measured by the same means (POCT or venous blood sampling) as done at baseline, and 3 months after enrollment.

9.1.2 Assessment of Secondary Outcomes

Please refer to chapters 5.2.

9.1.3 Assessment of Safety Outcomes

9.1.3.1 Adverse Events

We consider the risks of this study to be very low. Possible risks may occur if glycemic control cannot be achieved and maintained with lifestyle intervention. Consequently, the patient may experience symptoms of hyperglycemia requiring further medical attention. Patients will be systematically questioned about the occurrence of AEs at each study visit. The patients' safety will be monitored by assessment of blood sample parameters and the recording and evaluation of all study related AEs.

9.1.3.2 Laboratory Parameters

Laboratory parameters to be monitored for patient safety will be blood glucose, glycated hemoglobin A1c, pH, bicarbonate and base excess.

9.1.3.3 Electrocardiography

Patients will receive electrocardiographic diagnostics before enrollment into the study if deemed necessary by the treating physician.

9.1.3.4 Vital Signs

Blood pressure, heart rate and body weight will be measured at each study visit. Additionally, blood pressure will be measured during bicycle intervention in 15-minute intervals. The intervention will be stopped if systolic pressure exceeds 240 mmHg. A member of the study team will be present at all times during the bicycle exercise.

Please refer also to chapter 5.2.

9.1.4 Assessments in Participants who Prematurely Stop the Study

Patients who prematurely withdraw from the study will be substituted. Withdrawal will be documented in the database with all other study data. Follow-up will not take place if the patient has withdrawn informed consent, in all other cases follow-up will take place as planned.

Procedures at Each Visit

9.1.5 Visit 1: Day 0 – Initial Consultation

All Patients will be recruited at the ER department or outpatient clinic of a participating study center or by their personal practitioner after presenting with a newly diagnosed or untreated type 2 diabetes mellitus. The treating physician will assess whether the patient is clinically fit to participate in the study and will order an ECG if necessary.

If the patient meets all of the inclusion and none of the exclusion criteria, he or she is required to sign the ICF. The patient will then be randomized 1:1 to the intervention or the control group.

Medical history is taken followed by a physical examination and drawing of blood samples for a venous blood gas analysis (pH, pCO₂, base excess, bicarbonate, glucose) and a baseline HbA1c (may be up to 14 days old).

Patients allocated to the intervention group will then perform a 30-minute bicycle exercise at 60 % of the age-adjusted maximal heart rate. Blood samples will again be drawn at the end of the exercise as well as 30 and 90 minutes after its completion to determine blood glucose levels and to do a venous BGA at 90 minutes after the bicycle exercise.

All participants of the intervention group will receive a structured plan for an intensive lifestyle intervention for the following 3 months as well as an actigraph provided by the DSBG to monitor daily physical activity between study visits.

Patients allocated to the control group will receive the standard diabetes care practiced at the study center according to national and international guidelines.

Patients will be discharged when clinically stable and no comorbidities require further hospitalization.

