5. STUDY OUTCOMES

5.1 Primary Outcome

The primary endpoint of this study is achievement of metabolic control with intensive lifestyle intervention 3 months after study enrollment. For the purpose of this study, metabolic control is defined as a fasting glucose < 7.6 mmol/l and an HbA1c below a target stratified for three groups according to HbA1c at baseline: HbA1c > 14 % → target < 10 %; HbA1c < 14 % and > 10 % → target < 8 %; HbA1c < 10 % → target < 7.5 %.

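### Visit 1 prints history, examination and any new baseline HbA1c after open randomisation; fix one HbA1c before allocation, and separately settle the analysis set and replacement rule

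*Protocol*

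**What the plan says.** Protocol Section 9.1.5 (Visit 1) runs in this order. The treating physician judges fitness. Then: "If the patient meets all of the inclusion and none of the exclusion criteria, he or she is required to sign the ICF". Next: "The patient will then be randomized 1:1 to the intervention or the control group". The following paragraph reads: "Medical history is taken followed by a physical examination and drawing of blood samples", the samples being for a venous blood gas and "a baseline HbA1c (may be up to 14 days old". Intervention patients then ride.

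HbA1c has two roles. Section 7 requires at least 7.5% for entry. Section 5.1 defines the primary endpoint through "an HbA1c below a target stratified for three groups according to HbA1c at baseline": below 7.5% for a baseline under 10%, below 8% for 10 to 14%, and below 10% for a baseline over 14%. Section 9.1.1 has the 3-month value "measured by the same means (POCT or venous blood sampling) as done at baseline". Section 6.1.2 states: "Blinding of patients and study personal is not possible for this study".

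The schedule tables for both arms list history, the entry criteria, physical examination and HbA1c in rows above randomisation, all under day 0.

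On a separate matter, the synopsis (Statistical Considerations) names a per-protocol basis, while Section 11.1.1 names intention to treat. Section 7 allows patients who discontinue to be replaced, and Section 9.1.4 says that they will be. Section 8 (withdrawn participants) and Section 11 (missing data and drop-outs) both say that they will not.

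**The concern.** In an unblinded trial, whatever decides entry or defines the outcome should be on record before the arm is known. The Visit 1 text reads as a sequence, and it puts history, examination and any fresh HbA1c after allocation. Several exclusion criteria depend on history or examination, such as previous anti-diabetic medication, earlier lifestyle intervention, blood pressure and fever. The HbA1c also decides which target the patient must reach.

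The part that matters statistically is the HbA1c. If the value that admitted the patient and the value that sets the target are two measurements, and the second is read once the arm is known, there is room for a choice between them. For a patient close to 10% or 14% that choice changes the target.

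The analysis-set conflict is a different problem. It decides who is counted in the primary comparison, whatever the order of Visit 1.

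**Working it through.** **1. The plan's own figure.** No figure in the plan depends on the order of Visit 1. The sample size (80% against 40%, two-sided alpha 0.05, 80% power) reproduces: the normal approximation with continuity correction gives 28 per group, and 23 without it. Exact Fisher power at 28 per group is 82.3%. With 10% loss, 56 × 1.10 = 61.6, so 62. The change proposed below leaves this untouched.

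**2. Which HbA1c counts.** Sections 7 and 9.1.5 allow three situations.

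- *The entry value is at most 14 days old and nothing new is drawn.* One value serves both roles and is known before allocation. Visit order is then irrelevant to it.
- *The entry value is at most 14 days old and a new one is also drawn.* The older value is permitted as baseline but not required. Two values qualify, and the text does not say which sets the target.
- *The entry value is older than 14 days.* Section 7 puts no age limit on it. The criterion "Type 2 diabetes diagnosed within the last two years according to the ADA-criteria" dates the diagnosis, not the HbA1c. The 14-day limit in Section 9.1.5 would then call for a new draw and point to that draw as baseline. As printed, the target-setting value is first known after allocation, and nothing says what happens if it falls below 7.5%.

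**3. What hangs on the choice near a cut-off.** Targets are from Section 5.1.

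- At 10% the target moves by 8 − 7.5 = 0.5 points. Two readings of 9.9% and 10.1% require falls of more than 9.9 − 7.5 = 2.4 and 10.1 − 8 = 2.1 points.
- At 14% it moves by 10 − 8 = 2.0 points. Readings of 13.9% and 14.1% require falls of more than 13.9 − 8 = 5.9 and 14.1 − 10 = 4.1 points.

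These steps belong to the endpoint cut-offs and would exist under any visit order. They show why the value should be fixed early; they do not measure bias from Visit 1. A different target changes a patient's result only if the 3-month HbA1c lies between the two targets and, under Section 5.1, fasting glucose is also below 7.6 mmol/l.

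**4. The analysis set, taken separately.** Assume full enrolment, 62/2 = 31 per arm, and the planned 80%, so 0.80 × 31 = 24.8 expected responders.

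- Intention to treat: 24.8/31 = 80.0%.
- Per-protocol, with one intervention patient removed whose chance of success was s: (24.8 − s)/30. For s = 0.8 this is 80.0% (no change); for s = 0.4, 81.3% (+1.3 points); for s = 0, 82.7% (+2.7 points).

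The values of s are assumptions that span a range. The result illustrates the synopsis wording only. It is not an effect of Visit 1 order: under Section 8 an incomplete ride is merely documented, and follow-up continues unless consent is withdrawn.

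**The case against.** The strongest reply is that the protocol already requires all criteria to be met before consent and randomisation. HbA1c is one of them, so a value must be known by then. A baseline value that may be up to 14 days old cannot always have been drawn after a same-day randomisation, so the paragraph may simply list the contents of Visit 1. The row order of Tables 1 and 2 supports that, and Figure 1, which is not available here, may show it. HbA1c does not change within hours, and the draw precedes the ride, so allocation cannot alter the result itself. A rule for choosing among baseline values could also sit in an analysis plan.

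Most of this stands, and it limits the point. It does not remove it. The text uses sequence words throughout, row order is not stated to be time order, and no sentence makes the entry value the baseline value. An analysis plan can name the baseline value, but when it is recorded relative to allocation is a matter of trial conduct, which this protocol section governs.

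A reader might infer more: that ineligible patients would be randomised, or that staff would pick the convenient reading. The documents support neither. Eligibility can be established from routine care and a recent HbA1c, and nothing suggests selection between values.

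It is also fair to say that the analysis set and replacement rules do not arise from Visit 1. They are treated here as a separate correction.

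**Conclusion.** Two conclusions of different strength.

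*Visit 1 order* is a minor weakness and a cheap improvement. No bias is demonstrated. With a single HbA1c fixed before allocation, and intention to treat, the effect is zero. Otherwise it depends on how often two values exist on either side of 10% or 14%, which the documents do not give and which is not guessed here. For history and examination, no consequence for the primary result has been shown; recording them first only brings the text into line with the tables.

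*Analysis set and replacement* are wrong as written. The protocol gives two incompatible populations for one primary comparison, and incompatible replacement rules. The shift of 0 to 2.7 points per removed patient applies only if the synopsis wording were followed, and rests on the assumed success chances.

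**What to change.** In Section 9.1.5, move the baseline paragraph ahead of randomisation and state: *History, physical examination and one HbA1c, not older than 14 days and with its date and method recorded, are entered before randomisation. This single HbA1c is used both for eligibility and for the primary-endpoint target.* The blood gas is not an entry criterion and need only precede the ride.

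This costs no patients and leaves the sample size and power unchanged. It has two downsides: a 14-day limit on the entry HbA1c, which Section 7 does not now impose, and a short wait when no recent value exists.

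Separately, change the synopsis to intention to treat, with every randomised patient kept in the allocated arm. Align Sections 7 and 9.1.4 with the no-replacement rule in Sections 8 and 11. The substitution of pregnant participants in Section 10.1.2 needs the same alignment. These are text changes only.

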9.1.6 Visit 2-6: Day 2/7/30/60/90 – Study Visits

At each study site the study visits will take place at the respective endocrine or medical polyclinic. Study visit 2 will be combined with specific diabetes consultation where patients learn how to measure their blood glucose.

Further study visits will be combined with regular check-ups for newly diagnosed diabetes patients.

1. Vital signs (heart rate, blood pressure and body weight) will be measured at any study visit
2. Patients will be questioned about the occurrence of AEs or other difficulties with the conduct of the study at any study visit
3. HbA1c will be measured at visits 5 and 6
4. Intervention group participants will be instructed in correct self-measurement of blood glucose by a member of the study team at study enrollment or on visit 2 and will receive a blood glucose monitor to document fasting glucose every morning during the first week of the study
5. Patients will be instructed on when and how to measure their blood glucose at home by the diabetes counseling. For the study they will be asked to write down a diurnal profile of their blood glucose measurements three days before each study visit in addition to their regular measurements. For the diurnal profile fasting glucose in the morning as well as before each principal meal should be measured. To increase adherence they will receive reminders from the study team by telephone
6. The self-evaluation of the lifestyle intervention will be discussed with the patient at visit 2
7. Home measured blood glucose values will be discussed with the patients of the intervention group at any study visit
8. SIMPAQ and SF-36 questionnaires will be filled out at visit 2
9. In between visits 2-6 weekly coaching by phone will be held to improve the adherence to the lifestyle interventionActigraph readout will be conducted at visit 6
10. Re-hospitalizations and unplanned physician consultations will be assessed through questioning at visit 6 in both arms
11. Participants allocated to the control group will be monitored at 3 and 6 months after study entry. This means they do not participate in visits 2-5 and will only be seen by the study team for visit 6 and 7 after enrollment. They will therefore not be as closely monitored as the intervention group and will not receive weekly phone calls by the study psychologist

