Study Product/Intervention:	
Patients will be randomized either to standard care or to a bicycle exercise followed by an intensive lifestyle intervention on top of non-pharmacological standard care.
 
After rehydration, patients allocated to the intensified lifestyle intervention group will be instructed to perform 30 minutes of bicycle exercise at 60 % of the calculated maximum heart rate (according to Franckowiak et al.)²⁰ followed by an intensive lifestyle intervention. Patients will be discharged if the clinical status is stable and no comorbidities require further hospitalization. Follow-up visits at the Clinic of Endocrinology for further instructions and consultation will be carried out after 2, 7, 30, 60 and 90 days, half a year and a year.
 
In order to monitor blood glucose levels, patients will be instructed on visit 2 to take measurements at home and will be asked to send their fasting glucose levels of the first week to the study team for monitoring of the metabolic situation. This will also be done in the week before visits of day 30 and 90.
 
The schedule for the intervention arm consists of 3 to 5 aerobic training sessions (duration 15-40 minutes each) and 2 resistance trainings per week, as well as weekly motivational coaching via telephone by the study psychologist. Everyday activity will be objectively monitored using the patient's mobile phone and a blinded actigraph (activity tracker). Exercise sessions will be monitored by weekly phone calls and documented. To assess baseline physical activity all patients will fill in the SIMPAQ questionnaire at baseline and at 6 months.

Control Intervention (if applicable):	
The control arm will consist of the standard care delivered by the involved centers.

Number of Participants with Rationale:	The aim of this study is to assess whether bicycle exercise followed by an intensive lifestyle intervention can sufficiently restore metabolic control without anti-diabetic drugs at 3 months after study enrollment as compared to a standard of care control group. Based on our clinical experience we expect that 80 % in the intervention group will reach the primary endpoint of metabolic control with no anti-diabetic drugs compared to only 40% in the usual care control group. The inclusion of 28 patients per group (n total 62 patients including 10 % lost to follow-up) will provide 80 % power at an alpha level of 0.05.

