SUSAR	Suspected unexpected serious adverse reaction
TMF	Trial master file

STUDY SCHEDULE

Study Periods	ER	Intervention Period								Follow-up	Telephone FU
Visit	1	2	3		4		5		6	7	8
Time (day)	0	2 +/- 1	7 +/- 3	weekly	30 +/- 7	weekly	60 +/- 14	weekly	90 +/- 14	180 +/- 14	1 year +/- 45
Patient information and informed consent	x										
Demographics	x										
Medical history	x										
Medication	x				x		x		x	x	x
ECG (electrocardiograph)	(x)										
In- /exclusion criteria	x										
Physical examination	x										
Vital signs	x	x	x		x		x		x	x	only weight
Fasting blood samples (including glucose, insulin and c-peptide)		x							x	x	
Glycated hemoglobin A1c	x						x		x	x	x
Randomization	x										
Bicycle intervention	x										
Diabetes counselling (i. e. general information, self glucose measurements)		x	(x)								
Nutrition counselling			x								
Telephone (coaching) interview				x		x		x			
Report about physical activity (SIMPAQ)		x								x	
Adverse events	x	x	x		x		x		x	x	
Actigraph readout			x						x	x	
Quality of life questionnaire SF-36		x								x	
Start of Metformin therapy									(x)		

Table 1 Study schedule of the intervention group. (x) optional

Study Periods	ER	standard care period	Follow-up	Telephone FU
Visit	1	6	7	8
Time (day)	0	90 +/- 14	180 +/- 14	1 year +/- 45
Patient information and informed consent	x			
Demographics	x			
Medical history	x			
Medication	x	x	x	x
ECG (electrocardiography)	(x)			
In- /exclusion criteria	x			
Physical examination	x			
Vital signs	x	x	x	only weight
Fasting blood samples (including glucose, insulin and c-peptide)	x	x	x	
Glycated hemoglobin A1c	x	x	x	x
Randomization	x			
Diabetes counselling (i. e. general information, self glucose measurements)	(x)	x		
Nutrition counselling	(x)	x		
Report about physical activity (SIMPAQ)	x		x	
Adverse events	x	x	x	
Quality of life questionnaire SF-36	x		x	
Start of Metformin therapy	(x)	(x)		

Table 2 Study schedule of the control group. (x) optional

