5.2 Secondary Outcomes

Secondary outcomes are as follows:

- Absolute HbA1c reduction per stratification group (groups consist of HbA1c > 14 %, HbA1c < 14 % and > 10 % and HbA1c < 10 %)
- Change of HbA1c at 6 and 12 months after enrollment compared to control group
- Proportion of patients achieving target per stratified group after 3 and 6 months without anti-diabetic medication other than Metformin
- Changes in pH, base excess and bicarbonate 90 minutes after bicycle exercise compared to baseline
- Change of weight at 3, 6 and 12 months after enrollment compared to baseline and to standard of care
- Changes in blood glucose at the end of, as well as 30 and 90 minutes after bicycle exercise compared to baseline
- Feasibility of bicycle exercise at study enrollment in the ER, defined as absence of problem reports through the study team (e.g. patient cooperation)
- Safety of bicycle exercise, defined as:
 - o Absence of SAEs during the exercise
 - o No signs of acute cardiopulmonary decompensation in the patient during bicycle exercise
 - o No necessity to prematurely terminate the bicycle intervention because of other health or safety concerns
- Safety of intensive lifestyle intervention within 3 months following study enrollment, with the following endpoints:
 - o Number of SAEs in the intervention group compared to the control group
 - o Number of rescue medication administered in the intervention group compared to the control group
- Length of initial hospitalization, as well as number and length of re-hospitalizations and unplanned re-consultations within 3 months after initial consultation
- Changes in physical activity at 6 months compared to baseline assessed by SIMPAQ questionnaire (Endpoint: hours of physical activity)
- Changes in physical activity at 3 and 6 months compared to baseline assessed by actigraph (Endpoint: Stepgoal reached)
- Number of anti-diabetic medication at 30, 60, 90 days, as well as 6 months and one year compared to baseline in both arms
- Proportion of patients receiving insulin therapy after 6 months and one year in the intervention group compared to the control group
- Absolute health-care related costs at 3, 6 and 12 months in both arms
- Quality of life at 6 months in the intervention group compared to standard of care as assessed by SF-36 questionnaire.

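### The intervention arm's baseline SIMPAQ and SF-36 are taken at visit 2, after allocation and the start of the intervention, while controls complete theirs on day 0

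*Protocol*

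**What the plan says.** The synopsis (Study Product/Intervention) sets the intention: "To assess baseline physical activity all patients will fill in the SIMPAQ questionnaire at baseline and at 6 months". Section 5.2 then names as a secondary outcome "Changes in physical activity at 6 months compared to baseline assessed by SIMPAQ questionnaire". For SF-36, section 5.2 asks for a comparison of the arms at 6 months, section 4.3 speaks of comparing changes in quality of life, section 9.1.7 item 4 reads both forms against baseline, and section 11.1.3 tests the arms against each other at baseline and at 6 months.

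The schedule differs by arm. In section 9.1.6, item 8 reads "SIMPAQ and SF-36 questionnaires will be filled out at visit 2". Item 11 says of the controls: "This means they do not participate in visits 2-5 and will only be seen by the study team for visit 6 and 7". Table 1 (intervention) marks both questionnaires at visits 2 and 7 and leaves visit 1 blank. Table 2 (control) marks them at visits 1 and 7.

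Section 9.1.5 puts these steps on day 0. After consent, "The patient will then be randomized 1:1 to the intervention or the control group". The intervention arm then does the 30-minute bicycle exercise, and "All participants of the intervention group will receive a structured plan for an intensive lifestyle intervention for the following 3 months". Section 6.1.2 adds: "Blinding of patients and study personal is not possible for this study".

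**The concern.** A baseline should be measured before allocation can influence it, and in the same way in both arms. Here the intervention arm reports its activity and quality of life knowing its allocation, after an exercise session meant to change how patients see physical activity, and with a training plan in hand. Section 9.1.6 item 6 also has the self-evaluation of the lifestyle intervention discussed at that same visit.

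If the first answer in one arm already reflects the intervention, the change from it to 6 months does not measure the same thing in the two arms. The between-arm test of SF-36 at baseline is then not a check of comparability before treatment either. This is fixed at data collection: no later analysis plan can recover a pre-intervention value that was never obtained.

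**Working it through.** The protocol states no figure on this point, so the check is of timing.

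**1. Visit mapping, from Tables 1 and 2.**

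| Item | Intervention (Table 1) | Control (Table 2) |
|---|---|---|
| Randomisation | visit 1, day 0 | visit 1, day 0 |
| Bicycle exercise | visit 1, day 0 | not applicable |
| First SIMPAQ and SF-36 | visit 2, day 2 ± 1 | visit 1, day 0 |
| Second SIMPAQ and SF-36 | visit 7, day 180 ± 14 | visit 7, day 180 ± 14 |
| Actigraph readout | visits 3, 6, 7 | not scheduled |
| Medication record | visits 1, 4, 5, 6, 7, 8 | visits 1, 6, 7, 8 |

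The tables and section 9.1.6 agree, so this is the design as written and not a misread table. The intervention arm's first questionnaire falls on days 1 to 3. The order of the controls' day 0 questionnaires relative to randomisation is not stated.

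**2. Is follow-up length the problem?** Visit 7 falls on days 166 to 194.
- Intervention: 166 − 3 = 163 to 194 − 1 = 193 days.
- Control: 166 − 0 = 166 to 194 − 0 = 194 days.

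The intervals are nearly equal, so length is not the issue. What happened before the first answer is.

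**3. Share of the recall window after allocation.** For a form completed d days after allocation with a recall period of R days, the share is min(d/R, 1). The protocol lists both instruments in section 17 by title only, so R is an assumption. With d = 1 to 3:
- R = 1 day: 100%.
- R = 7 days: 1/7 = 14% to 3/7 = 43%.
- R = 28 days: 1/28 = 4% to 3/28 = 11%.

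For controls on day 0 the share is about 0% throughout.

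**4. How many patients can still benefit.** The inputs are first patient in 11/2018, last patient out 12/2025, follow-up of 1 year (+ up to 45 days), and version date 30.10.2023. From 1.11.2018 to the version date is 1824 days. The last enrolment then falls 2177 days (1.12.2025 minus 1 year and 45 days) to 2252 days (31.12.2025 minus 1 year) after the start. The elapsed share is 1824/2252 = 81% to 1824/2177 = 84%. With even recruitment of 62 patients (an assumption), 16–19% remained, or about 10–12 patients.

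**5. Two smaller mismatches in the same schedule.**
- Sections 6 and 8.1.3 call the first actigraph readout baseline. Table 1 puts it at visit 3 (day 7 ± 3, days 4 to 10), on a device issued on day 0 together with the plan. It therefore records the first week of the intervention.
- Section 5.2 wants medication counts in both arms at 30, 60 and 90 days, 6 months and one year. Table 1 schedules 5 of these 5 points. Table 2 schedules 3 of 5, with none at days 30 and 60.

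**The case against.** The scheduling fact is hard to dispute; its weight is not. By days 1 to 3 the intervention arm has had one exercise session, a plan and an actigraph. Nutrition counselling comes at visit 3, and the weekly calls start after visit 2. With a long recall period little of the window is affected. Controls may also answer knowing their arm, since section 9.1.5 randomises directly after consent. The SF-36 outcome in section 5.2 is a 6-month level, and for SIMPAQ section 11.1.3 speaks only of comparing the medians of the two groups. Most patients were probably enrolled by version 1.10, and if SIMPAQ is compared on 6-month levels, a moved questionnaire adds nothing to that comparison.

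Much of this stands as a limit on size and reach, and the 100% figure applies only if recall is one day. It does not remove the problem. Section 5.2 defines the SIMPAQ outcome as a change, and sections 4.3 and 9.1.7 read SF-36 the same way. Unstated order in the controls is a further gap, not a defence, and the difference in exposure to the exercise and the plan remains. The 6-month level comparison gives up baseline information in a trial of 62, which is a real cost. It is nevertheless valid by randomisation, which a comparison on mismatched baselines is not. Moving the forms still gives later patients a true baseline.

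The actigraph and medication points are minor. The actigraph endpoint is step-goal attainment, so only the label and the comparison with baseline are touched. Section 6 foresees routine visits in both groups that could supply medication data, and section 11.1.3 compares medication between arms only at 3 and 6 months.

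**Conclusion.** The concern holds and should be corrected. The intervention arm's first SIMPAQ and SF-36 come 1 to 3 days after open allocation and after the intervention has begun; the controls' come on day 0. No pre-intervention value is scheduled for the intervention arm.

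Confidence in the timing is high. The size and direction of any bias cannot be derived: they depend on the recall periods, which the protocol does not show, and on how far knowledge of allocation and the first session shift self-report. The recall shares and the count of remaining patients rest on the assumptions given with them.

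The effect is confined to the secondary SIMPAQ change outcome, any SF-36 change comparison and the SF-36 baseline test. The primary endpoint, HbA1c, weight, the 6-month SF-36 level comparison and step-goal attainment at 3 and 6 months are not affected.

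**What to change.** **Schedule.** In Table 1, Table 2, section 9.1.5 and section 9.1.6 item 8, have both questionnaires completed at visit 1, after consent and before randomisation, in both arms. This moves the intervention arm's forms and fixes the order for controls.

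**Patients already enrolled.** Flag the visit 2 values as post-randomisation and state the limitation. Base the between-arm SIMPAQ comparison on 6-month levels for all patients, so that two kinds of baseline are not mixed, and align sections 5.2 and 11.1.3 with this. Keep the planned 6-month SF-36 level comparison, and do not present the SF-36 baseline test as a pre-treatment check.

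**Minor.** Relabel the visit 3 actigraph readout as week 1 of the intervention in sections 6, 8.1.3 and 11.1.3, and do not use it as a pre-intervention value. Reconcile the medication outcome in section 5.2, the synopsis (Measurements and Procedures) and section 6 with Table 2, for example by recording start and stop dates of each anti-diabetic drug at visit 6 in both arms.

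**Cost.** Controls already complete both forms on day 0, so the burden per patient is small. The schedule change reaches only later enrolments: about 10–12 patients in all, of whom about half (5–6) would be in the intervention arm under 1:1 allocation. The rest is wording, plus start and stop date entries for each drug at visit 6.
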